3.3 SELECTION OF TRIAL POPULATION

Approximately 222 participants are planned to be randomised into the trial, in order to have approximately 180 participants evaluable for the primary analysis. It is planned that about 45 trial centres in 2 countries (USA and Japan) will be participating in this trial to ensure a sufficient number of participants are randomised.

It is expected that approximately 4-8 participants will be randomised at each trial centre. If enrolment is delayed, additional sites may be recruited. To avoid differential centre influence on trial results, permission to randomise more than 15 participants per site must be obtained from the sponsor, CTL or designee. This will only be allowed after a careful review of the enrolment status and the site.

Screening of participants for this trial is competitive, i.e. screening for the trial will stop at all centres when such a number of participants have been screened that it can be anticipated that a sufficient number of participants will be randomised to trial treatment. Investigators will be notified about screening completion and will then not be allowed to screen additional participants for this trial. Participants already in screening at this time will be allowed to continue to randomisation if eligible.

A log of all participants screened for the trial (i.e. who have signed informed consent) will be maintained in the ISF, irrespective of whether or not IMP was administered to the participant.

The following information, at minimum, will be collected, including for participants who are determined to be ineligible for randomisation: participant number, visit date, demographics, eligibility criteria, information on AEs (if applicable), and concomitant treatment relevant for the AE.

If retrospectively it is found that a trial participant has been randomised in error (i.e. did not meet all the inclusion criteria or met one of more exclusion criteria), the sponsor or delegate should be contacted immediately. Based on an individual benefit-risk assessment, a decision will be made as to whether continued trial participation is possible.

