7.2 PLANNED ANALYSES

7.2.1 General considerations

Statistical analyses will be based on the following main analysis sets:

- Treated set (TS):
The TS includes all participants who were randomised and treated with the IMP. The TS will be used for safety and most of the efficacy analyses. Safety analyses will be conducted using actual treatment received. For efficacy analyses, treatment assignment will be as randomised, unless specified otherwise.
- Primary analysis set (PAS)
The PAS comprises all randomised participants who received at least one dose of IMP during the trial and had a baseline MADRS total score ≥ 24 . The primary analysis will be performed on the PAS and will be based on assigned treatment.

Further analysis sets may be specified in the TSAP.

In general, baseline will be defined as the last available value prior to the first administration of the IMP. Further details will be provided in the TSAP.

Adherence to the protocol will be assessed by the trial team. Important protocol deviations (iPDs) categories and how to handle iPDs in the analysis will be specified in the SDTM DV domain specifications, which are stored in the TMF. The iPD categories will be updated as needed. Also, the extent and impact of the receipt of incorrect trial medication will be assessed. Details will be specified in the TSAP.

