7.2.3 Primary objective analyses

7.2.3.1 Main analyses

As defined in Section 2.1.2, the primary endpoint is the change from baseline to Week 6 in MADRS total score.

MCPMod (multiple comparison and modelling techniques) [R10-1424] is used to evaluate several possible dose response models (patterns). As a basis for the MCPMod analysis, a restricted maximum likelihood estimation (REML) based on a mixed-effect model for repeated measures (MMRM) analysis will be used to generate covariate adjusted estimates of mean change from baseline in MADRS total score at Week 6 and associated covariance matrices. The model will include fixed categorical effects of treatment at each visit and number of antidepressant treatments taken for the current episode (0 versus 1), and fixed continuous effects of baseline MADRS total score at each visit. Participants from the PAS with a baseline and at least one post-baseline value with their MADRS values of all post-baseline visits will be included in the model, according to the considered strategy for handling intercurrent events.

The primary treatment comparisons will be the contrasts between each BI 1569912 treatment arm and placebo at Week 6. Procedures to be followed if the planned analysis fails to converge will be described in the TSAP.

The dose-response relationship of these estimates from the MMRM will then be analysed using MCPMod. Thereby, several possible dose response models (patterns) will be evaluated (while keeping full control of the type I error at 10%, one-sided) to identify the best-fitting model or subset of models.

A monotone dose-response relationship is assumed. For the PoCC testing and for the sample size calculations the following model assumptions ([Table 9](#)) and resulting graphs ([Figure 2](#)) have been selected to cover both the plausible and a diverse range of potential dose response patterns.

Table 9 Dose response pattern assumptions and rationale

Model	Description
Linear	Linear dose response
Emax1	50% of the maximum effect (ED50) is achieved at the 5 mg dose
Emax2	95% of the maximum effect (ED95) is achieved at the 10 mg dose
Exponential	5% of the maximum effect is achieved at the 5 mg dose, i.e. high effect only at a high dose
Sigmoid Emax	20% of the maximum effect (ED20) is achieved at the 5 mg dose, 80% of the maximum effect (ED80) is achieved at the 10 mg dose, i.e. effect of 5 mg and 10 mg are further apart (fixed hill parameter h=4)

[figure not shown]
[figure not shown]

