7.4 RANDOMISATION

Participants will be randomly assigned in a 2:1:1:2 ratio to one of these treatment groups:

1. Placebo
2. 5 mg BI 1569912 qd
3. 10 mg BI 1569912 qd
4. 20 mg BI 1569912 qd

Randomisation will be stratified by baseline MDD severity, defined as baseline MADRS total score < 24 versus ≥ 24 , region (USA versus Japan), and number of antidepressant treatments taken for the current episode (0 versus 1).

Boehringer Ingelheim will arrange for the randomisation and the packaging and labelling of trial IMP. The randomisation list will be generated using a validated system, which involves a pseudo-random number generator so that the resulting treatment will be both reproducible and non-predictable. Specific parameters used for the creation of the randomisation schedule (e.g. block size) will be documented in the CTR. Access to the codes will be controlled and documented.

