7. PLANNED ANALYSIS

For End-Of-Text tables, the set of summary statistics is:

N	number of non-missing observations
Mean	arithmetic mean
SD	standard deviation
Min	minimum
Q1	1 st quartile
Median	median
Q3	3 rd quartile
Max	maximum

Tabulations of frequencies for categorical data will include all possible categories and will display the number of observations in a category as well as the percentage (%) relative to the

respective treatment group (unless otherwise specified, all participants in the respective participant set whether they have non-missing values or not).

The precision for percentages should be one decimal point. The category missing will be displayed only if there are actually missing values.

Any p-value presented will be from two-sided tests and confidence intervals (CI) will be two-sided 95% CI, unless otherwise specified. Apart from the p-values from the primary test for a flat dose response relationship on change from baseline in MADRS total score at Week 6, all p-value presented will be considered descriptive (nominal) in nature.

Analyses performed by treatment group will consider the following treatment groups:

- Placebo,
- 5 mg BI,
- 10 mg BI,
- 20 mg BI,
- BI total (where applicable), and
- Total (where applicable).

Thereby, summary tables of disposition, demographics and other baseline characteristics data, as well as descriptive summaries of safety data, including treatment compliance and treatment exposure data, and descriptive summaries of efficacy data will in general include a BI total and a total column.

For model-based analyses, unless stated otherwise, the actual strata “number of antidepressants used for the current episode” (0 vs 1) and “baseline MADRS total score” (< 24 vs ≥ 24) as documented in the eCRF will be used, as applicable. If erroneous data was documented and used for randomisation in IRT, this will be described accordingly – but these erroneous data will in general not be used for the model-based analyses.

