7.5 PRIMARY OBJECTIVE ANALYSIS

7.5.1 Main analysis

CTP Section 7.2.3.1:

[...] *the primary endpoint is the change from baseline to Week 6 in MADRS total score.*

[MCPMod is used for the primary analysis of the primary endpoint – to test the null hypothesis that there is a flat dose response curve comparing placebo and the BI 1569912 dose groups on the primary endpoint.]

MCPMod (multiple comparison and modelling techniques) [ref. 9.17] is used to evaluate several possible dose response models (patterns). As a basis for the MCPMod analysis, a restricted maximum likelihood estimation (REML) based on a mixed model for repeated measures (MMRM) analysis will be used to generate covariate adjusted estimates of mean change from baseline in MADRS total score at Week 6 and associated covariance matrices. The model will include fixed categorical effects of treatment at each visit and number of antidepressant treatments taken for current episode (0 versus 1), and fixed continuous effects of baseline MADRS total score at each visit.

The Kenward-Roger approximation will be used to estimate denominator degrees of freedom and adjust standard errors (SEs). Least-squares mean estimates per dose group and differences to placebo at each time point, corresponding two-sided 95% CIs and p-values will be presented in tables. Further, for the differences to placebo at each time point, standardized effect sizes will be calculated based on the results/estimates of this analysis (standardized effect size = (adjusted mean difference in change from baseline between treatment groups) / (SE / sqrt(1/n + 1/m)), where n and m are the number of participants in the respective treatment group).

Additionally, adjusted means and corresponding SEs will be presented graphically over time.

For the MMRM, an unstructured covariance matrix will be assumed. In case of non-convergence the following steps will be taken (in that order) to overcome convergence issues:

1. Add the 'singular=1e-10' option in the model statement
(This raises the threshold at which columns are declared linearly dependent (from typically 1e-12).)
2. Set 'maxiter=100' in the Proc Mixed statement
(This increases the number of convergence iterations used from a default of 50.)
3. Set 'scoring=4' to specify use of the Fisher scoring algorithm in the first 4 iterations.
4. Include the statement 'performance nothread'
(This removes multi-threading, possibly improving stability, but may also slow down calculations.)

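### Region (USA versus Japan) is the only randomisation stratum absent from the primary MMRM; if it predicts MADRS change, the MCPMod test is slightly conservative, and adding it by visit costs little

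*SAP*

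**What the plan says.** Protocol 7.4 stratifies randomisation by baseline MADRS total score (below 24 versus 24 or above), "region (USA versus Japan), and number of antidepressant treatments taken for the current episode (0 versus 1". Protocol 3.3 explains why region is a factor: "It is planned that about 45 trial centres in 2 countries (USA and Japan) will be participating in this trial".

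The primary model does not carry all three. Protocol 7.2.3.1: "The model will include fixed categorical effects of treatment at each visit and number of antidepressant treatments taken for the current episode (0 versus 1", followed by "and fixed continuous effects of baseline MADRS total score at each visit". SAP 7.5.1 repeats the same list: "The model will include fixed categorical effects of treatment at each visit and number of antidepressant treatments taken for current episode", again with baseline MADRS by visit. SAP section 7, in stating which strata enter model-based analyses, names "the actual strata “number of antidepressants used for the current episode” (0 vs 1" and baseline MADRS, again without region.

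The MADRS stratum is accounted for twice. The primary analysis set admits only participants who "received at least one dose of IMP during the trial and had a baseline MADRS total score ≥ 24", and baseline MADRS is also a continuous covariate. The antidepressant stratum is a model term. Region is therefore the one stratum with no counterpart in the primary analysis.

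The covariance matrix estimated by this MMRM is what MCPMod uses, both to update the contrasts and to test them (protocol 7.2.3.1, SAP 7.5.1).

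**The concern.** Stratifying on region balances it across arms, so variation between regions largely drops out of the true sampling variance of a dose-versus-placebo contrast. A model without region still counts that variation as residual error. When region is prognostic, the reported standard error then exceeds the true one, the maximum-contrast statistic is too small, and the test rejects less often than its nominal level allows. The same standard errors sit behind the 95% confidence intervals for each dose against placebo.

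At stake is a small amount of efficiency in a trial whose planned success probability is about 82%, set against a correction that uses a factor already collected and already balanced by design.

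**Working it through.** **1. Reproduce the plan's figure.** Inputs from protocol 7.5 and Table 10: SD 10, maximum difference −4, 60/30/30/60 evaluable, one-sided 10%, five candidate shapes. With the shape percentages read relative to the 20 mg effect, the optimal contrasts equal SAP Table 9 for Linear and Emax1 and agree within about 0.006 for the other three. The multivariate-t critical value with 180 − 4 = 176 degrees of freedom is 1.609. Simulated average success probability is 82.4% at −4 and 93.3% at −5; the protocol states 82.4% and 93.3%.

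**2. Effect of omitting region.** Let p be Japan's share and g the difference between regions in mean change at Week 6. Neither is in the documents, so both are assumptions. Holding the total SD at 10:

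- within-region SD = √(100 − p(1 − p)g²)
- standard error overstated by 10 / (within-region SD) − 1

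Example, p = 0.5 and g = 4: √(100 − 0.25 × 16) = √96 = 9.798, and 10/9.798 = 1.021, so 2.1% too large.

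| p | g | Within-region SD | SE too large by | Type I error | Success at −4, region omitted | Region included |
|---|---|---|---|---|---|---|
| 0.2 | 0 | 10.000 | 0% | 10.0% | 82.4% | 82.4% |
| 0.2 | 2 | 9.968 | 0.3% | 9.9% | 82.5% | 82.6% |
| 0.2 | 4 | 9.871 | 1.3% | 9.6% | 82.6% | 83.2% |
| 0.3 | 4 | 9.831 | 1.7% | 9.5% | 82.7% | 83.4% |
| 0.5 | 4 | 9.798 | 2.1% | 9.4% | 82.8% | 83.6% |
| 0.5 | 6 | 9.539 | 4.8% | 8.6% | 83.2% | 85.1% |
| 0.5 | 7 | 9.367 | 6.8% | 8.2% | 83.7% | 86.3% |

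The last row's error rate and success probabilities come from a separate simulation of the same test.

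**3. Check by simulating stratified trials** (20,000 per scenario; 20 mg versus placebo, where the formula at SD 10 gives 10 × √(1/60 + 1/60) = 1.826):

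| p | g | True SE | Model SE, no region | Model SE, with region |
|---|---|---|---|---|
| 0.2 | 0 | 1.823 | 1.825 | 1.825 |
| 0.2 | 4 | 1.799 | 1.826 | 1.802 |
| 0.5 | 6 | 1.734 | 1.827 | 1.741 |

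**4. Would a single region main effect be enough?** Steps 2 and 3 treat Week 6 as the only time point, whereas the MMRM spans Day 8 and Weeks 2, 4 and 6. Suppose the regional difference grows as 1, 2, 3.5 and 5 points over those visits, with SDs of 6, 7.5, 9 and about 10, p = 0.3 and complete data (all assumptions). Omitting region overstates the Week 6 standard error by 10/√(100 − 0.21 × 25) − 1 = 2.7%. A common region effect is estimated mainly from the earlier, less variable visits and misses part of the Week 6 difference. In a large-sample generalised least squares calculation the remaining overstatement is 1.0–1.5% under autoregressive correlation of 0.5–0.8 and 1.4–3.1% under compound symmetry of 0.5–0.8. At the top of that range it is no better than leaving region out. Region by visit removes it.

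**The case against.** The strongest reply is that the consequence is conditional. Standard errors are too large only if region predicts Week 6 change after adjustment for baseline MADRS and number of antidepressants, and the documents contain no evidence on that. This stands. A reader might infer from the omission alone that the standard errors are wrong; with g = 0 they are not. Protocol 5.6.3 links duplicate enrolment to raised placebo rates and says the duplicate check will not be run in Japan. That is a reason the regions could differ, but it says nothing about the size or direction.

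Second, a reader might infer that the trial is underpowered or its error rate inflated. Neither follows. The sample size rests on a total SD of 10, with no credit described for covariates, and success probability with region omitted stays at or above the stated 82.4% in every scenario. The error runs only in the conservative direction, so the 10% limit holds.

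Third, protocol and SAP give the same covariate list. This is a consistent pre-specified choice and not a contradiction between documents. That also stands; what is missing is a reason for it.

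Finally, the models for other endpoints and the subgroup section (SAP 6.5) are not visible, so no claim can be made that region is missing there. Nothing in those sections would alter the primary model as written.

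**Conclusion.** The point holds as an unexplained omission with a small, conditional cost. Region is a stratum in protocol 7.4 and is not reflected in the primary MMRM in either document. If the regions differ by up to 4 points in adjusted mean change, with Japan at 20–50%, the Week 6 standard errors are 0–2.1% too large, the one-sided type I error is between 10% and 9.4%, and adding region gains under 1 percentage point of average success probability at −4. Gains of about 2 to 2.6 points need a 6–7 point difference and an even split, which is extreme beside a planned placebo change of −9 and a maximum drug effect of −4. These gains assume that the model captures the Week 6 regional difference in full, which a main effect alone does not guarantee. The change is worth making because it is nearly free, not because the planned result is at risk.

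**What to change.** Before unblinding:

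- In protocol 7.2.3.1 and SAP 7.5.1, add region (USA versus Japan) as a fixed categorical effect by visit, that is, region and region-by-visit. Use this model for the Week 6 adjusted means and covariance matrix that feed MCPMod.
- In SAP section 7, add region to the strata named for model-based analyses.
- Record the change in SAP section 4.

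The cost is one degree of freedom for each of the four post-baseline visits, two or three lines of text, and no new data. If the sponsor prefers to keep the present model, a sentence giving the reason for leaving out a stratification factor would close the point.

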7.5 DETERMINATION OF SAMPLE SIZE

The study is intended to show a benefit of BI 1569912 over placebo in terms of the difference in change from baseline in MADRS total score at Week 6.

The aim of this study is to show a significant non-flat dose-response curve across the different doses and placebo. The probability of success of this trial is therefore defined as the probability to obtain a significant test for non-flat dose-response curve.

The sample size calculation is based on an assumed maximum difference in change from baseline in MADRS total score of BI 1569912 vs. placebo of ≤ -4 at Week 6, as well as on the pre-specified models listed in Section 7.2.3.1. The standard deviation of change from baseline in MADRS total score is assumed to be 10 (i.e. the assumed maximum difference of ≤ -4 corresponds to a standardised effect size of ≤ -0.4). For placebo, a fixed rate of -9 change from baseline in MADRS total score at Week 6 will be considered.

The following calculations and presented operating characteristics use a sample size of 180 evaluable patients with a baseline MADRS total score ≥ 24 (assigned to placebo and low to high dose regimes, respectively, in a 2:1:1:2 ratio). Adjusting for a drop-out rate of approximately 18% (randomised patients not included in the PAS, or without primary endpoint assessment), the total sample size required is then approximately 222 (with 74/37/37/74 per dose group).

Using a total sample size of 180 evaluable patients, the probability for a successful trial (as defined above) was estimated using simulations. For each dose group, samples of the required size were drawn from a normal distribution.

Based on these assumptions, if the maximum difference between active doses and placebo is -4, the success probability is approximately 82% on average across the different considered dose response models. The probability to observe an effect of at least -3.5 in the trial is 65%. If the maximum difference between active doses and placebo is -5, the success probability is approximately 93% on average across the different considered dose response models. In this case, the probability to observe an effect of at least -3.5 in the trial is 83%.

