If the difference between active doses and placebo is low, i.e. -1 (which is assumed to be clinically not relevant), the success probability is approximately 23% on average. The probability to observe an effect of at least -3.5 in the trial is 10%. In the case that there is no treatment benefit, the false positive probability is limited by the α -level for the significance testing of the non-flat dose-response curve of 10% (one-sided).

[Table 10](#) provides success probabilities under different scenarios (i.e. different treatment effects and dose-response curves).

Table 10 Success probability given expected change from baseline in MADRS total score at Week 6 and a total sample size of 180 patients (with 60/30/30/60 per dose group) based on MCPMod nominal alpha-level of 10% (one-sided).

Scenario	(Assumed) true model											
Expected max. resp. diff. (BI-Plac)	Linear		Emax1		Emax2		Exponential		Sigmoid Emax		Average	
	(1)	(2)	(1)	(2)	(1)	(2)	(1)	(2)	(1)	(2)	(1)	(2)
-5	92.2	81.5	92.4	81.3	93.8	84.2	93.7	83.7	94.1	84.4	93.3	83.0
-4	81.1	63.9	81.4	63.6	83.5	65.7	82.7	65.8	83.3	66.1	82.4	65.0
-3	62.3	41.6	64.1	42.4	66.2	44.6	63.9	43.8	65.2	44.1	64.3	43.3
-2	42.3	23.1	42.3	23.4	42.4	23.4	42.9	23.7	44.1	23.9	42.8	23.5
-1	22.3	9.2	22.9	10.2	23.6	10.2	22.8	10.1	23.2	9.7	22.9	9.9
0	9.5	3.1	10.2	3.7	9.9	3.4	9.9	3.4	9.8	3.2	9.9	3.3

(1) success probability (%): significant non-flat dose-response achieved based on at least one of the candidate set models (one-sided α -level of 10%),

(2) probability (%) to observe a response difference of at least -3.5 compared with placebo for at least one modelled dose within the considered dose range.

Probabilities have been calculated using R Version 4.0.1 based on simulations (10000 simulations per scenario). Thereby the calculations for the MCPMod step have been performed using DoseFinding R-package 1.0-2.

8. INFORMED CONSENT, TRIAL RECORDS, DATA PROTECTION, PUBLICATION POLICY, AND ADMINISTRATIVE STRUCTURE

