5. Provide starting values for covariance parameters using a 'parms' statement.

6. Should none of the previous methods work, the covariance matrix will be changed from unstructured to Toeplitz with heterogeneous variances (TOEPH). Should this also not converge, a standard Toeplitz matrix (TOEP) will be fitted. Finally, if convergence still does not occur, then an order-1 autoregressive matrix (AR(1)) will be fitted.

CTP Section 7.2.3.1:

Participants from the PAS with a baseline and at least one post-baseline value with their MADRS values of all post-baseline visits, will be included in the model, according to the considered strategy for handling intercurrent events [(see Section 6.3) Note that the MMRM automatically excludes observations of participants without a baseline and at least one post-baseline value from analysis.]

The primary treatment comparisons will be the contrasts between each BI 1569912 treatment arm and placebo at Week 6.

The dose-response relationship of these estimates from the MMRM will then be analysed using MCPMod. Thereby, several possible dose response models (patterns) will be evaluated (while keeping full control of the type I error at 10%, one-sided) to identify the best-fitting model or subset of models.

A monotone dose-response relationship is assumed. For the PoCC testing and for the sample size calculations the following model assumptions (Table 8) and resulting graphs [Figure 1] have been selected to cover both the plausible and a diverse range of potential dose response patterns.

Table 8: Dose response pattern assumptions and rationale

Model	Description
Linear	Linear dose response
E_{max1}	50% of the maximum effect (ED₅₀) is achieved at the 5 mg dose
E_{max2}	95% of the maximum effect (ED₉₅) is achieved at the 10 mg dose
Exponential	5% of the maximum effect is achieved at the 5 mg dose, i.e. high effect only at a high dose
Sigmoid E_{max}	20% of the maximum effect (ED₂₀) is achieved at the 5 mg dose, 80% of the maximum effect (ED₈₀) is achieved at the 10 mg dose, i.e. effect of 5 mg and 10 mg are further apart (fixed hill parameter h=4)

[figure not shown]

Figure 1: Shape and considered dose response patterns for the MCPMod analysis

The optimal contrasts corresponding to the candidate models [are shown in the following table (see [Section 10.5](#) for the R code used for the calculation)].

Table 9: Contrast coefficients

[figure not shown]

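### The last two covariance fallbacks for the primary MMRM (TOEP, AR(1)) impose one variance on all visits, so if they are reached and variance rises towards Week 6, the 10% type I error is exceeded

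*SAP*

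**What the plan says.** SAP 7.5.1 bases the primary test on an REML MMRM of MADRS change from baseline. It has treatment by visit, baseline by visit, the number of prior antidepressants, an unstructured covariance and Kenward-Roger adjustment. For non-convergence it lists five numerical remedies (singularity tolerance, iterations, Fisher scoring, threading, starting values). Step 6 then changes the structure, first to Toeplitz with heterogeneous variances (TOEPH), and if that also fails: "a standard Toeplitz matrix (TOEP) will be fitted. Finally, if convergence still does not occur, then an order-1 autoregressive matrix (AR(1)) will be fitted".

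The MMRM estimates and their covariance matrix go into MCPMod, where the five candidate shapes are tested "keeping full control of the type I error at 10%, one-sided". The text available to us names no empirical (sandwich) standard error for any fallback.

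SAP Table 4 sets the post-baseline MADRS target days at 8, 15, 29 and 43. On variability, Protocol 7.5 gives one figure: "The standard deviation of change from baseline in MADRS total score is assumed to be 10". Read in context, this is the Week 6 value. No SD is given for the earlier visits.

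**The concern.** TOEP and AR(1) estimate one residual variance across the four visits. The Week 6 standard error then reflects roughly the average of the visit variances and not the Week 6 variance itself. If spread grows during treatment, that average is too small at the one time point that matters. Kenward-Roger adjusts for estimating the covariance parameters in a finite sample. It takes the structure as given and does not correct a wrong one.

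Because MCPMod divides its contrasts by these standard errors, an understated Week 6 value makes the proof-of-concept test anti-conservative. A prespecified rule could then breach the error control stated in the same section.

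**Working it through.** **Inputs from the documents.** One-sided 10% error over five shapes (SAP 7.5.1); Week 6 SD 10, and 180 evaluable participants "with 60/30/30/60 per dose group" (Protocol 7.5); visits on Days 8, 15, 29 and 43 (SAP Table 4).

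**Assumed inputs.** The SDs at Day 8, Week 2 and Week 4, and the between-visit correlations. Both are varied below.

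**Step 1: reproduce the plan's figures.** Optimal contrasts were computed for the five shapes with weights 60/30/30/60. They match SAP Table 9 exactly for Linear and Emax1 and to within 0.006 for the others. With SD 10 and 176 degrees of freedom (180 − 4), the max-t critical value is 1.61. Average power at a maximum difference of −4 is 82.3%, against 82.4% in Protocol Table 10. Size at zero effect is 10.0%, against 9.9%.

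**Step 2: the Week 6 SD that a common variance implies.** To a close approximation it is the root mean square of the four visit SDs. For 8/9/9.5/10:

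√[(64 + 81 + 90.25 + 100)/4] = √83.81 = 9.15, a ratio to the true value of 0.915.

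For 5/7/9/10:

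√[(25 + 49 + 81 + 100)/4] = √63.75 = 7.98, a ratio of 0.798.

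**Step 3: convert the ratio to size.** Size = P(max T > 1.61 × ratio) under the null, with 1,000,000 draws. The ratios below come from the best-fitting (Kullback-Leibler) TOEP and AR(1) matrices with complete data. Four correlation patterns were used: constant 0.6; 0.8 per 7 days; 0.9 per 7 days; and 0.7 per visit step.

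| Assumed SD, Day 8/Week 2/Week 4/Week 6 | Modelled/true Week 6 SE | True size |
|---|---|---|
| 10/10/10/10 (flat) | 1.00 | 10.0% |
| 8/9/9.5/10 | 0.91–0.92 | 12.7–12.9% |
| 7/8/9/10 | 0.86 | 14.7–14.8% |
| 5/7/9/10 | 0.79–0.80 | 17.2–17.4% |
| 12/11/10.5/10 (falling) | 1.09–1.10 | 7.4–7.6% |

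TOEP and AR(1) agree to within 0.1 percentage point of size. Adding 15% monotone dropout moves the steepest case to about 18%.

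**Step 4: finite-sample check.** A null simulation with REML fits (3,000 trials per scenario, complete data, correlation 0.9 per 7 days) gave 10.1% (flat), 12.1% (8/9/9.5/10), 15.5% (7/8/9/10) and 7.2% (falling) for TOEP and AR(1). The unstructured fit gave 9.1% to 10.0%.

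**Step 5: isolate visit spacing.** The gaps are 7, 14 and 14 days, while these structures let correlation depend only on visit order. With constant variance and correlation decaying in calendar time, the size under TOEP and AR(1) was 10.0–10.1%. Spacing alone does not inflate the error.

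**Step 6: structures with visit-specific variances.** Under the same scenarios, TOEPH and heterogeneous AR(1) gave Week 6 SE ratios of 1.00 to 1.04 and sizes of 8.8% to 10.0%, whatever the SD pattern.

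**Covariance parameters with four visits:** unstructured 10; TOEPH 4 + 3 = 7; ANTE(1) 4 + 3 = 7; heterogeneous AR(1) 4 + 1 = 5; TOEP 1 + 3 = 4; AR(1) 1 + 1 = 2.

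**The case against.** The strongest reply is that the premise is not in the documents. Nothing says that variance rises over visits, and the flat and falling cases give correct or conservative error. That stands, and it makes the point conditional. There is a reason to expect a rise. The model adjusts for baseline at each visit, so what matters is the residual variance given baseline, and that grows if the correlation with baseline weakens. With constant score variance and illustrative baseline correlations of 0.7/0.6/0.5/0.4, the residual SD is proportional to √(1 − r²). Scaled to 10 at Week 6, this gives about 7.8/8.7/9.4/10, close to the 13% scenario. This makes a rise plausible but does not establish it.

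The second reply is that the step is remote. With four time points and about 180 evaluable participants, the unstructured fit will very likely converge. Five numerical remedies and TOEPH must fail before TOEP is tried, and TOEP must fail before AR(1). That also stands, and it keeps the priority low.

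Third, the SAP did what the protocol asked: it prespecified a convergence procedure, and its first structural fallback keeps visit-specific variances. This is true of TOEPH, but the next step drops that protection.

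A reader might infer that TOEP and AR(1) necessarily understate the Week 6 standard error, or that the uneven visit spacing is to blame. The documents support neither. The direction depends on SDs they do not give, and spacing alone left the size at 10%.

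**Conclusion.** The point holds in conditional form, as a low-priority improvement. If TOEP or AR(1) is reached and the SD of MADRS change rises to 10 at Week 6 (over the range 8/9/9.5/10 to 5/7/9/10), the Week 6 standard error is understated by about 9% to 20%. The true one-sided size is then about 13% to 17% against the stated 10%. With a flat SD the size is 10%; with a falling SD (12/11/10.5/10) it is about 7.4%.

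These figures rest on assumed earlier-visit SDs and correlations. Nothing here bears on the planned unstructured analysis or on the power figures in Protocol 7.5.

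**What to change.** In step 6 of SAP 7.5.1, keep visit-specific variances in every fallback: after TOEPH, replace TOEP and AR(1) with heterogeneous AR(1) (ARH(1)) and retain Kenward-Roger. At 5 parameters it is a real simplification of TOEPH (7). ANTE(1) also has 7, so it is a less useful next step after a TOEPH failure.

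If TOEP or AR(1) is kept as a final backstop, state that empirical (sandwich) standard errors will be used with a compatible degrees-of-freedom method. In large samples this restores a correct standard error with complete data, but it was not simulated here. It also does not repair point estimates that depend on the covariance structure when data are missing.

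The cost is one SAP sentence and one program option. The downsides are a slightly conservative test in some scenarios under heterogeneous structures (about 9%), one more covariance parameter than TOEP or three more than AR(1), and loss of Kenward-Roger if the sandwich backstop is used.
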